3.2.4 Monthly time intervals

A month is defined as 30 days and time intervals based on monthly durations are defined as a multiple of 30 days (eg, 12 months is defined as 360 days). The definitions of 3- and 6-month

intervals are based on the durations in [Table 3–2](#), which use 30-day months where EV relative days as defined in Section [3.2.1.2](#) will be used:

Table 3–2: Definition of monthly interval durations during the first year

Interval	EV relative days
Months 1 to 3	1 to 90
Months 4 to 6	91 to 180
Months 7 to 9	181 to 270
Months 10 to 12	271 to 360
Months 1 to 6	1 to 180
Months 7 to 12	181 to 360

Subsequent 3 and 6-month intervals, and 12-month intervals are defined in a similar manner.

Three-month intervals will be calculated for summaries and analyses of efficacy and safety outcomes scheduled to be assessed at each MEV, FEV, YEV and FV. A subject is included in the analysis for a 3-month interval if the end of their evaluation period is on or after the final day of the 3-month interval and the seizure diary was completed for at least 1 day during the 3-month interval.

Six-month intervals will be calculated for summaries and analyses of efficacy and safety outcomes scheduled to be assessed at each FEV, YEV and FV, but not each MEV. Similar to the approach for inclusion in 3-month summaries detailed above, a subject is included in the analysis for 6-month intervals if the end of their evaluation period is on or after the final day of the 6-month interval and the seizure diary was completed for at least 1 day during the 6-month interval.

Six and 12-month intervals will be calculated for analyses of seizure freedom. For further information on subject inclusion into these calculations, see Section [3.10.3.1](#).

For the analysis of AEs, a subject is included in the analysis for a 3-month interval if the end of their evaluation period is on or after the first day of the 3-month interval.

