For subjects ≥ 2 years of age with typical absence seizures categorization, response is based on the 1-hour EEGs performed over the Evaluation and Down-Titration Period separately.

Calculation of Seizure freedom

The categorical variable Seizure freedom is defined to be equal to 1 if none of the EEG assessments within the reported time period (Evaluation Period or Down-Titration Period) have shown occurrence of any seizures and 0 otherwise.

For subjects < 2 years of age seizure freedom is based on the 24-hour EEGs performed over the Evaluation and Down-Titration Period separately.

For subjects ≥ 2 years of age with typical absence seizures categorization, seizure freedom is based on the 1-hour EEGs performed over the Evaluation and Down-Titration Period separately.

Calculation of Seizure freedom rate

Seizure freedom rate will be determined as follows:

$$\text{Seizure freedom rate of Time Period} = 100 \times \left[\frac{\text{Number of subjects who were seizure free over reported Time Period}}{\text{Number of subjects who entered reported Time Period with at least one evaluable EEG assessment during the Time Period}} \right]$$

The denominator includes only those subjects applicable, depending on age group and seizure categorization. See calculation of Seizure freedom.

Calculations based on DRC data

DRC data will be analyzed for DE and LTFU subjects.

Calculation of average daily frequency (ADF) of seizures and 28-day adjusted seizure frequency

Average daily frequency (ADF) of seizures based on the DRC data is calculated over the Evaluation Period, by visit and by 3-month time intervals:

$$ADF = \frac{\sum_{i=1}^n \text{seizure count entered at day } i}{n},$$

where n is the number of days with non-missing seizure count entry in the DRC during the reporting time period. The reporting time period includes the start date but excludes the stop date of the time period.

For DE subjects, Baseline ADF will take DRC data from ScrV to TV1 into account only. For LTFU subjects, Baseline diary data is obtained from Baseline of the core study.

The ADF will be calculated including counts for all seizure types and additionally for POS seizures only.

The 28-day adjusted seizure frequency is calculated as:

$$\text{28day adjusted seizures frequency} = \text{ADF} \times 28$$

The Baseline 28-day adjusted seizure frequency will be calculated using the Baseline ADF.

The 28-day adjusted POS seizure frequency will be calculated using the POS ADF respectively.

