Criterion 1: A subject completed the reported Time Period

- Up-Titration Period: for DE subjects only, if at least one eCRF during Up-Titration Period is entered (only Baseline/TV1, Baseline/TV1 and TV2 or Baseline/TV1, TV2 and TV3 could be entered, dependent on subject's individual titration)
- Evaluation Period: if the FV or EDV eCRF page (named FIN) is entered
- Down-Titration Period: if the eCRF DTV page is entered (DTV is the final visit for the Down-Titration Period)

Criterion 2: The seizure diary was completed for at least 90% of days from start date of the appropriate Time Period up to the day prior to the end date of the appropriate Time Period.

Criterion 3: All entered seizure codes have a count of 0 from the day after start date of appropriate Time Period (ie, not including the start date of appropriate Time Period) up to and including the end date of the appropriate Time Period. (If a seizure code is entered, a missing count will lead to a violation of this criteria, too.)

If one of the criteria is not fulfilled, Seizure freedom is defined to be equal to 0.

Seizure freedom will be based on DRC data collected over the Up-Titration, Evaluation and Down-Titration Period separately. All seizure types will be taken into account.

Calculation of Seizure freedom rate

Seizure freedom rate will be determined as follows:

$$\text{Seizure freedom rate of Time Period} = 100 \times \left[\frac{\text{Number of subjects who were seizure free over reported Time Period}}{\text{Number of subjects who entered reported Time Period with at least one DRC entry during the Time Period}} \right]$$

All seizure types will be taken into account.

Calculation of Seizure freedom by visit

The categorical variable Seizure freedom by visit is defined to be equal to 1 if the following criteria are fulfilled:

Criterion 1: The question "Have there been any seizures since the last visit?" has been answered with "No" and all entered seizure codes in the DCR have a count of 0 since prior visit. (If a seizure code is entered, a missing count will lead to a violation of this criteria, too.)

Criterion 2: The seizure diary was completed for at least 90% of days since prior visit. The percentage of days for which diary data were entered since the prior visit will be calculated as follows:

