$$\% \text{ of days diary was done} = 100 \times \left[\frac{\text{Days since prior visit} - \text{number of days diary was not done in the interval}}{\text{Days since prior visit}} \right]$$

If one of the criteria is not fulfilled, Seizure freedom by visit is defined to be equal to 0.

Seizure freedom by visit will be based on DRC data and eCRF data collected over the Up-Titration, Evaluation and Down-Titration Period separately. All seizure types will be taken into account.

Calculation of seizure freedom by time interval

The categorical variable Seizure freedom by time interval is defined to be equal to 1 if the following criteria are fulfilled:

Criterion 1: All entered seizure codes have a count of 0 from the day after start date of appropriate time interval (i.e., not including the start date of appropriate time interval) up to and including the end date of the appropriate time interval. (If a seizure code is entered, a missing count will lead to a violation of this criteria, too.)

Criterion 2: The seizure diary was completed for at least 90% within the time interval. The percentage of days for which diary data was completed within a given 6-month interval will be calculated as follows based on a 30-day month:

$$\% \text{ of days diary was done} = 100 \times \left[\frac{180 - \text{number of days diary was not done in the interval}}{180} \right]$$

A similar calculation applies for 3-month seizure freedom based on 90 days and 12-month seizure freedom based on 360 days.

If one of the criteria is not fulfilled, Seizure freedom by time interval is defined to be equal to 0.

Seizure freedom by time interval will be based on DRC data collected over the Up-Titration, Evaluation and Down-Titration Period separately. All seizure types will be taken into account.

Calculation of Incidences for new seizure types

To calculate incidences of new seizure types and subtypes a shift table from Present at Baseline (Yes, No, Missing, Total) to Present during Evaluation Period (Yes, No, Missing, Total) will be prepared. Subjects who do not have results for subtypes at Baseline will be presented with “not assessed” Baseline results and their respective Evaluation Period result. Whenever only subtype information is available the seizure type results will be derived as follows:

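### Three-month seizure freedom skips the first day of each interval, so a seizure on Day 91, 181 or 271 counts against no 3-month interval

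*SAP*

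**What the plan says.** SAP Section 3.2.4 counts days from the Entry Visit (EV) and sets 3-month intervals that abut: after Days 1 to 90 come "Months 4 to 6 91 to 180", "Months 7 to 9 181 to 270" and "Months 10 to 12 271 to 360". The 6-month intervals are "Months 1 to 6 1 to 180" and "Months 7 to 12 181 to 360". Twelve months is 360 days, and later intervals follow the same pattern.

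SAP Section 3.10.3.1 then places different windows on these intervals:

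- **Seizure freedom by time interval, Criterion 1.** All seizure counts must be zero from the day after the start, "not including the start date of appropriate time interval", through the end date.
- **Seizure freedom by time interval, Criterion 2.** Diary completion must reach 90%, with a denominator of 90, 180 or 360 days, which is the full interval.
- **ADF from the daily record card (DRC).** The reporting period "includes the start date but excludes the stop date of the time period". This rule serves the Evaluation Period, by-visit and 3-month results alike.
- **Proportion of seizure-free days.** It is also reported by 3-month interval, with no endpoint rule of its own.

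Section 3.10.3.1 defines interval seizure freedom for 3, 6 and 12 months. Section 9.2 names only the by-visit and 3-month summaries, restricted to subjects under 2 years or those aged 2 years and over with typical absence seizures.

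**The concern.** Leaving out the start date does no lasting harm when one period's start date is also the previous period's end date, because the day is then checked once. Table 3-2 intervals share no day. A start day dropped from its own interval is not the end day of the one before, so it disappears from the 3-month series.

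The same subject and interval can then give two conflicting results: seizure-free on one variable and a positive seizure frequency on the other. Tables and listings programmed as written would show this. Checking fewer days can only raise the seizure-free proportion, so the error cannot average out.

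**Working it through.** The plan states no figure to reproduce; the check is an enumeration of days followed by a bound on the effect.

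**Step 1. Windows.** Take the intervals from Table 3-2, extended in the same pattern. The seizure-freedom window is [start + 1, end]. The DRC ADF window, read literally, is [start, end − 1].

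| Interval | Seizure-freedom window | DRC ADF window (3-month only) |
|---|---|---|
| 1–90 | 2–90 | 1–89 |
| 91–180 | 92–180 | 91–179 |
| 181–270 | 182–270 | 181–269 |
| 271–360 | 272–360 | 271–359 |
| 1–180 | 2–180 | – |
| 181–360 | 182–360 | – |
| 1–360 | 2–360 | – |

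**Step 2. Which days escape the seizure-freedom check.**

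| Day | 3-month | 6-month | 12-month |
|---|---|---|---|
| 1 | missed | missed | missed |
| 91 | missed | checked (2–180) | checked (2–360) |
| 181 | missed | missed | checked (2–360) |
| 271 | missed | checked (182–360) | checked (2–360) |
| 361 | missed | missed | missed |

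Day 1 is the EV date under Section 3.2.1.2, so leaving it out may be deliberate. The later days have no such reason.

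**Step 3. One subject.** Suppose the diary is complete and the only seizure in Months 4–6 is on Day 91.

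- Seizure freedom: all counts are zero on Days 92–180 and diary completion is 100 × (90 − 0)/90 = 100%, so the subject is seizure-free.
- ADF: Day 91 lies in 91–179, which has 89 days, so ADF = 1/89 = 0.011 per day, or 28/89 = 0.31 per 28 days.

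The two results contradict each other.

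**Step 4. Size.** The documents give no seizure rate or distribution. As an assumption, let seizures be Poisson with daily rate r = (rate per 28 days)/28. Checking 89 days instead of 90 changes the 3-month seizure-free proportion from exp(−90r) to exp(−89r).

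| Rate per 28 days | exp(−90r) | exp(−89r) | Absolute gain (points) | Relative gain |
|---|---|---|---|---|
| 0.25 | 44.8% | 45.2% | 0.40 | 0.9% |
| 0.5 | 20.1% | 20.4% | 0.36 | 1.8% |
| 1 | 4.0% | 4.2% | 0.15 | 3.6% |

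The gain exp(−89r) − exp(−90r) is largest where exp(−r) = 89/90. There it equals (89/90)^89 × (1/90) = 0.370/90 = 0.0041, or about 0.41 percentage points at any rate.

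**Step 5. ADF.** Read literally, the ADF windows omit Days 90, 180, 270 and 360. An omitted day leaves both the seizure sum and the day count n, so the omission does not push ADF in a fixed direction.

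**Step 6. With both end days included.** The 3-month windows become 1–90, 91–180, 181–270 and 271–360. No day is lost, and each window has the 90 days that the diary denominator assumes.

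**The case against.** Several points on the other side stand. The effect is under half a subject per 100. Section 2 calls all efficacy variables exploratory, there is one arm and no testing, and the named 3-month table covers a restricted group. The primary safety variables are untouched. The Poisson model is an assumption without support in the document.

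Three stronger readings are tempting, and the SAP does not support them:

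- **A subject with a seizure on Day 91, 181 or 271 is seizure-free in every interval.** The 6-month windows catch Days 91 and 271, and the 12-month window catches all three. The separate Evaluation Period variable also checks these days if they fall within the period. Of the days after Day 1 in the first two years, only Day 361 escapes all three lengths. The subject must also have no other seizure in the interval and meet the 90% diary criterion.
- **The ADF rule contributes to the missed seizures.** It does not, because Days 91, 181 and 271 lie inside the ADF windows. Its own gap is a separate inconsistency.
- **The Evaluation Period criteria contain the same error.** There, diary completion is counted "up to the day prior to the end date of the appropriate Time Period" while seizures are checked through the end date. That offset is defensible: Section 2.3.1 says no DRC is handed out at the Final Visit, and still counting a seizure on the last day is conservative.

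It can also be said that the stop or end date might mean the first day of the next interval. Table 3-2 does not say so, and it would not remove the conflict. ADF would cover 1–90 and seizure freedom 2–91, so a Day 91 seizure would count against Months 1–3 for freedom and in Months 4–6 for ADF.

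**Conclusion.** The point holds for interval seizure freedom, chiefly at 3 months. As written, the rule fails to check the first day of every 3-month interval, of every 6-month interval (including Day 181) and of every 12-month interval (including Day 361), although the diary denominator counts those days and the 3-month ADF includes them. The misclassification is always favourable. It is at most about 0.4 percentage points for a 3-month interval, given the Poisson assumption and a literal reading of Table 3-2. The loss of each interval's last day from ADF is a lesser inconsistency with no fixed direction. This is a minor correction, worth making because the rule would otherwise produce conflicting results for the same subject and interval.

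**What to change.** In Section 3.10.3.1, for Table 3-2 intervals after the first:

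- check seizures on every day from the interval's first day to its last, inclusive;
- use the same window for ADF, the proportion of seizure-free days and the diary-completion percentage.

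For the intervals that begin on Day 1 (first 3, 6 and 12 months), state once whether the EV date counts and apply that to all these variables. The diary denominators are then 90, 180 and 360 if Day 1 counts, or 89, 179 and 359 if it does not.

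Leave the Evaluation Period seizure-freedom criteria as they are. The cost is a few lines of SAP text and one date condition in the derivation program; no new data are needed.

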3.10.3 Seizures and seizure categories

Each seizure code in the clinical database will be mapped to exclusively 1 of the following seizure types based on the 1981 ILAE classification: IA, IA1, IA2, IA3, IA4, IB, IB1, IB2, IC, IIA, IIB, IIC, IID, IIE, IIF, or III.

With regard to cluster seizures, study sites are to report the number of cluster episodes rather than reporting the estimated number of individual seizures. Therefore, no imputation will be applied for the seizure counts corresponding to reports of cluster seizures. In all the efficacy analyses, clusters will be counted as one seizure (i.e. 1 cluster = 1 seizure) and assigned to the corresponding seizure type.

For the evaluation of this study the categorization of subjects to different seizure categories and the analysis by these seizure categories is essential.

Four different seizure categories need to be distinguished and defined:

- **POS – Partial-onset Seizure**

Subjects are categorized as POS subjects at ScrV if either Partial-Onset Seizure is entered on the “ILAE Seizure Classification History” eCRF page at ScrV or if it has been reported on “Historical Seizure Count” eCRF page for the last 3 weeks prior to ScrV with non-zero value.

- **PGS – Primary Generalized Seizure**

Subjects are categorized as PGS subjects at ScrV if either Typical Absence Seizure, Atypical Absence, Myoclonic, Clonic, Tonic, Tonic-clonic or Atonic Seizure is entered on the “ILAE Seizure Classification History” eCRF page at ScrV or if one of these seizure types has been reported on “Historical Seizure Count” eCRF page for the last 3 weeks prior to ScrV with non-zero value.

- **PGS* – Primary Generalized Seizure excluding Typical Absence**

Subjects are categorized as PGS* subjects at ScrV if either Atypical Absence, Myoclonic, Clonic, Tonic, Tonic-clonic or Atonic Seizure is entered on the “ILAE Seizure Classification History” eCRF page at ScrV or if one of these seizure types has been reported on “Historical Seizure Count” eCRF page for the last 3 weeks prior to ScrV with non-zero value.

- **Typical Absence Seizure**

Subjects are categorized as Typical Absence subjects at ScrV if either Typical Absence Seizure is entered on the “ILAE Seizure Classification History” eCRF page at ScrV or if it has been reported on “Historical Seizure Count” eCRF page for the last 3 weeks prior to ScrV with non-zero value.

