- Seizure type I is Present at Baseline = “Yes” if at least one of the subtypes IA, IB, IC is present at Baseline. It is Present at Baseline = “Missing” if data for all subtypes is missing. Otherwise, Present at Baseline = “No”.
(Same rule is to apply to summarize sub-subtypes IA1, IA2, IA3 and IA4 into IA. IA is Present at Baseline = “Yes” if at least one of the subtypes IA1, IA2, IA3 or IA4 is present at

Baseline. IA is Present at Baseline = “Missing” if data for all sub-subtypes is missing. Otherwise, Present at Baseline = “No”.)

- Seizure type II is Present at Baseline = “Yes” if at least one of the subtypes IIA, IIB, IIC, IID, IIE, IIF is present at Baseline. It is Present at Baseline = “Missing” if data for all subtypes is missing. Otherwise, Present at Baseline = “No”.
- Seizure type III does not have subtypes, so derivations are not applicable.

Incidences are the percentages for seizures which were not present at Baseline but present during Evaluation Period:

$$\text{Incidence of seizure type} = \frac{\text{Count of subjects with seizure (sub)type not present at Baseline but present in Evaluation Period}}{\text{Total number of subjects with seizure (sub)type not present at Baseline}}$$

Incidences will be calculated separately for Down-Titration Period.

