6.3 History of epilepsy

6.3.1 Epileptic seizure profile

The number and percentage of subjects experiencing each seizure category at any time prior to study entry will be summarized based on the ILAE Seizure Classification History eCRF.

The overall number and percentage of subjects with a history of Type I (POS), Type II (PGS), or Type III (Unclassified) seizures will also be summarized. A subject will be classified as having a history of Type I seizures if the subject has a history of Type IA, IB, or IC seizures. A subject will be classified as having a history of Type II seizures if the subject has a history of Type IIA1, IIA2, IIB, IIC, IID, IIE, or IIF seizures.

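### The new-seizure-type rule rolls sub-subtypes up for IA but not for IB1 and IB2, so a known focal seizure can be counted as new type I or new IB; the absence codes also disagree between sections

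*SAP*

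**What the plan says.** Section 3.10.3 states that each seizure code "will be mapped to exclusively 1 of the following seizure types": "IA, IA1, IA2, IA3, IA4, IB, IB1, IB2, IC, IIA, IIB, IIC, IID, IIE, IIF, or III". That is 16 codes. IB1 and IB2 stand beside IB as codes in their own right, just as IA1 to IA4 stand beside IA. Absence has the single code IIA.

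Section 3.10.3.1, under the calculation of incidences for new seizure types, introduces the roll-up with "Whenever only subtype information is available the seizure type results will be derived as follows". Type I is Yes "if at least one of the subtypes IA, IB, IC is present at Baseline", Missing if data for all subtypes are missing, and No otherwise. Type II is Yes "if at least one of the subtypes IIA, IIB, IIC, IID, IIE, IIF is present at Baseline", with the same handling of missing data. The only rule one level down is "Same rule is to apply to summarize sub-subtypes IA1, IA2, IA3 and IA4 into IA".

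The incidence is then defined: "Incidences are the percentages for seizures which were not present at Baseline but present during Evaluation Period". The denominator is the subjects in whom the type or subtype was not present at Baseline. Incidences are also to be calculated for the Down-Titration Period. Section 9.2 plans the shift tables.

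Section 6.3.1, on seizure history, builds type II from "history of Type IIA1, IIA2, IIB, IIC, IID, IIE, or IIF seizures". It uses IIA1 and IIA2, and not IIA.

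**The concern.** An incidence of new seizure types is only as good as its at-risk set. A child who already has a focal seizure should not be at risk of new type I. The authors saw that sub-subtypes need to be rolled up, wrote the rule in full for IA, and wrote none for IB. Since the mapping is exclusive, a seizure coded IB2 is not also coded IB, so nothing in the text carries it to IB or to type I. Programmed as written, the rule can put prevalent focal cases into both the denominator and the numerator.

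The absence codes raise a smaller question. Section 3.10.3 keeps typical and atypical absence apart when it assigns seizure categories, yet its code list and the roll-up have one absence code, and Section 6.3.1 has two.

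**Working it through.** The plan gives no figure for this derivation, so there is none to reproduce. The check compares the code lists and then applies the rule literally.

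**1. Code lists.**
- Codes in the Section 3.10.3 list with no place in the Section 3.10.3.1 roll-up: IB1 and IB2, and no others.
- Codes in Section 6.3.1 that are absent from the Section 3.10.3 list: IIA1 and IIA2, and no others.

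**2. One record.** Baseline: IB2 present, IA No, IC No, IB not recorded directly. None of IA, IB or IC is Yes and not all are missing, so type I is No and IB is not present. Evaluation Period: IC present, so type I is Yes. The literal result is 1 new type I case of 1 at risk. The child had a focal seizure at Baseline, so the right result is 0 cases and not at risk.

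**3. All single-code focal pairs.** The focal codes are IA, IA1 to IA4, IB, IB1, IB2 and IC: 1 + 4 + 1 + 2 + 1 = 9. Taking one code at Baseline and one in the Evaluation Period, with every other subtype recorded No, gives 9 × 9 = 81 pairs.
- Baseline codes that fail to reach type I: IB1 and IB2, so 2.
- Later codes that do reach type I: IA, IA1 to IA4, IB and IC, so 7.
- Pairs falsely counted as new type I: 2 × 7 = 14 of 81.
- Pairs falsely counted as new IB: IB1 to IB and IB2 to IB, so 2.
- With IB1 and IB2 rolled into IB, both counts fall to 0.

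These are counts of code patterns, not of children.

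**4. The reverse direction.** The rules are worded for presence at Baseline only. If the same rule is used for the Evaluation Period, a child with no focal seizure at Baseline and a first IB1 or IB2 seizure is not counted as new type I. That affects 2 of the 9 focal codes, and 0 after the fix.

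**5. Absence under one IIA code.** Let T be typical and A atypical absence.

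| Baseline | Evaluation | Truly new | Counted as new IIA |
|---|---|---|---|
| none | A, T, or both | yes | yes |
| T | A, or both | A | no |
| A | T, or both | T | no |
| T | T | none | no |
| A | A | none | no |
| both | A, T, or both | none | no |

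Of the 4 × 3 = 12 patterns, 3 + 2 + 2 = 7 contain a truly new absence type. Three of these are counted, as new IIA, and four are not. The type II result is unaffected, because either absence type makes type II present.

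**The case against.** The strongest reply is that the gap may never operate. The roll-up applies only where parent-level information is lacking. Section 6.3.1 builds type I history from IA, IB or IC, which is consistent with IB being recorded directly on the form. The exclusive mapping concerns seizure codes in the database and need not define the Baseline presence flags. Subjects without Baseline subtype results get their own not-assessed row. The forms and core-study datasets are not in the SAP, so this cannot be settled. It limits how often the error can occur. It does not supply the missing rule, since a parallel rule was thought necessary for IA.

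The conditions are also narrow. If IA or IC is present at Baseline, type I is correctly Yes. If IA, IB and IC are all missing, type I is Missing. A false case further needs a later IA, IB or IC seizure. A reader might infer that every child coded IB1 or IB2, or every child with absence seizures, is misclassified; the rule does not have that effect.

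A reader might also infer that new atypical absences are never counted. They are counted, as new IIA, when no absence type was present at Baseline. Nor is this table the plan's only view of aggravation by seizure type: Sections 2.2.3, 3.10.3.1 and 9.1 provide for worsening in generalized or other seizure types, and Section 2.2.3 lists the number and type of non-absence seizures in children with typical absence.

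Finally, reporting absence at IIA level could be a deliberate choice of detail, and the SAP never says what IIA1 and IIA2 are. That stands. What remains is that two sections use different codes without a definition.

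Classing a type as No when some subtypes are No and the rest missing is an explicit convention, and I do not press it. Replacing it with Missing unless all subtypes are No would, read literally, override a recorded Yes.

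**Conclusion.** The point holds in a limited form. Where only subtype information is available and IB is not recorded directly, a subject with IB1 or IB2 at Baseline, no IA or IC present, and at least one of these recorded No is classed as type I No and IB not present. A later IA, IB or IC seizure is then wrongly new type I, and a later IB wrongly new IB. If the same rule governs the Evaluation Period, a first IB1 or IB2 seizure is missed at type I level.

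The absence mismatch between Sections 3.10.3 and 3.10.3.1 on one side and Section 6.3.1 on the other is real. Its consequence is conditional: if IIA1 and IIA2 mean typical and atypical absence, which is an inference, then new atypical absence in a child with typical absence at Baseline, or the reverse, is not counted as a new subtype.

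The reach is small. The output is one descriptive efficacy shift table. New-seizure-type incidence is not among the variables listed in Sections 2.2.1 to 2.2.3, efficacy is exploratory, and nothing is tested. The number of subjects affected cannot be derived from the SAP. The change is still worth making, because the rule followed as written gives a wrong incidence and the correction is very cheap.

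**What to change.** - In Section 3.10.3.1, extend the sub-subtype rule so that IB1 and IB2 are summarized into IB in the same way as IA1 to IA4 into IA, keeping the present handling of missing data.
- State there that the same roll-up determines presence in the Evaluation Period and the Down-Titration Period.
- Use one set of absence codes in Sections 3.10.3, 3.10.3.1 and 6.3.1 and define each code. If typical and atypical absence are to be separate rows, add their codes to the mapping list and roll them up into IIA. If not, say that absence is reported only at IIA level.

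The cost is a few lines of SAP wording and a matching edit to the mapping table and program. No new data are needed.
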